The study, which brings together an experienced multidisciplinary team with expertise in telemedicine research, leverages the PCORnet National Patient-Centered Clinical Research Network (CRN) infrastructure through a collaboration among three CRNs and two health plans representing diverse urban and rural populations. Our aims are:

Aim 1: What are the features of primary care telemedicine programs newly implemented or expanded in response to the COVID-19 pandemic, and how is telemedicine offered to and experienced by diverse populations? In Aim 1A, we will conduct a comprehensive landscape survey of primary care leaders nationally, using a theory-informed survey instrument. Aim 1A will address an important knowledge gap on the extent and characteristics of telemedicine implementation during the COVID-19 pandemic. It will also provide crucial stakeholder-informed data about participating sites to support Aim 2. In Aim 1B, a qualitative study with patient and provider stakeholders will explore experiences with, barriers to, and facilitators of telemedicine and provide insights into disparities in delivery and use.

Aim 2: What is the comparative effectiveness of primary care telemedicine programs and capabilities on patient-centered outcomes and disparities in outcomes in chronic disease? In Aim 2A, we will apply natural experiment methods, leveraging CRN electronic health record (EHR) and claims data, to compare the effectiveness of (1) synchronous telemedicine alone; (2) telemedicine-supplemented in-person care; and (3) in-person care alone on patient-centered outcomes, including the quality of health care and the frequency of avoidable emergency department visits. In Aim 2B, we will examine how comparative effectiveness varies as a function of telemedicine program features (such as patient technical assistance and provider training). In Aim 2C, we will examine disparities in telemedicine use

PRINCIPAL INVESTIGATOR: [name]; [name]

and impact among patient subgroups, including socioeconomically vulnerable patient populations. Patient-reported outcomes include satisfaction with care and telemedicine usability.

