The study population encompasses patients that are attributed to primary care clinics in one of the four health systems defined above. Patients are included in the study if they are ages 19 or older and received two or more outpatient visits at a participating practice during a one-year period before the COVID-19 pandemic, and had one or more of five chronic illnesses (asthma, chronic obstructive pulmonary disease (COPD), congestive heart failure (CHF), diabetes, hypertension) as defined by the Medicare Chronic Conditions Warehouse algorithm.²⁷ For the claims analyses, we additionally require that patients are continuously enrolled over the entire study time period.

Interventions and Comparators

We will use natural variation in the availability of in-person and telemedicine visits across clinics over time during the pandemic in a difference-in-differences framework to compare the clinical effectiveness of three care models: (1) telemedicine-only; (2) telemedicine-supplemented in-person visits; and (3) in-person visits only.

While these arms will be defined at onset of the pandemic, clinics may not remain in the same arm over time. We will evaluate changes in total telemedicine and in-person visits in each month and capture the status of each clinic by month for secondary analyses. In additional secondary analyses, we will explore heterogeneity in effects across patient and organizational subgroups.

The intervention population encompasses patients that are attributed to primary care clinics that switched to delivering telemedicine-only visits as their primary model of care delivery during the pandemic. We will compare this population to patients that are attributed to clinics that delivered telemedicine-supplemented in-person visits or in-person visits only during the pandemic. We will define the clinics' primary model of care delivery, and the timing of their switch in clinical modality, using the survey results from Aim 1.

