Another complexity making it challenging to predict the directionality of the effect of the telemedicine transition is that the rapid nationwide transition appears to have led to diverse types of telemedicine programs, ranging from relatively mature programs with well-established technology and user support, to rapidly implemented programs with less well-established technology or support. This heterogeneity may influence whether telemedicine was effective in improving access to care or patient-provider communication. It is well-established that innovations that are not highly usable, well-matched to user needs, and supported with organizational support are unlikely to promote their desired outcomes.^{38,39}

In light of the complexities described above in the causal model, we propose a nondirectional overall hypothesis that telemedicine-only, telemedicine-supplemented in-person visits, and in-person only groups will have different healthcare utilization and patient satisfaction outcomes.

Primary Analysis

Our causal model will leverage variation over time and across sites in the availability of telemedicine visits to assess the impact of a change in clinic-level availability in telemedicine on patient-level outcomes. We will use a generalized version of the difference-in-differences methodology (also known as an event study design) in an intent-to-treat framework to compare patients receiving care at clinics that have switched to telemedicine-only visits at a given time with patients at comparable clinics that have not or that used a mixture of telemedicine and in person care. This event

PRINCIPAL INVESTIGATOR: [name]; [name]

study design allows for multiple treatment periods and for the relationship between treatment and outcomes to vary over time.

The causal identifying assumption in difference-in-differences models is that outcomes in each comparator arm would have followed the same trends in the absence of exposure to telemedicine, after the onset of the pandemic.⁴⁰ While we cannot directly test this assumption, we can test whether there significantly different trends in outcomes during the months prior to the onset of the pandemic. We expect that this parallel trends assumption may hold in our study, because the transition to telemedicine during the pandemic was rapidly implemented and potentially unrelated to patient outcomes and the underlying quality of the clinic.

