Primary findings will be presented alongside descriptive statistics assessing the external and internal validity of the analysis, including balance across relevant covariates before and after matching. We will also use descriptive statistics to characterize the analysis population, identify sources of missingness in the data across outcomes and covariates as well as whether missingness may introduce selection bias into our analysis. In sensitivity analyses, we will multiply impute covariates for which there is meaningful evidence of missingness.

Heterogenous Treatment Effects

We hypothesize that patients in disadvantaged sociodemographic groups will derive less benefit from telemedicine than patients in majority groups because of barriers to use of telemedicine described in the conceptual model. We additionally hypothesize that more robust telemedicine programs (as defined in the Aim 1 taxonomy) will provide more benefit to patients than less robust ones.

We will explore variation in effects for the outcomes listed in Table 1 among pre-specified sociodemographic subgroups (race/ethnicity, rurality, median income for zip code) and clinical subgroups (COVID-19 patients vs. all other patients; low vs. high burden of illness; stable vs. unstable disease, as indicated by clinical measures of disease progression). Finally, we will use the Aim 1 survey for stratified analyses of telemedicine factors, such as historical use of telemedicine and patient technical assistance. Additionally, the Medicare data will allow us to conduct a subgroup analysis for our claims-based outcomes on dually eligible patients. Therefore, we will conduct eight separate subgroup analyses in all. We will use the same analytic approach described in the primary analysis to conduct these subgroup analyses and present the differences in treatment effect estimates with standard errors. We will also conduct univariate subgroup analyses with interaction effects to statistically test for differences in outcomes (as outlined below) among these subgroups.

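### For features that presuppose a telemedicine program, stratifying the arm comparison leaves Aim 2B without a comparable contrast in each stratum

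*Combined protocol and SAP*

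**What the plan says.** Section B sets the Aim 2B question: "we will examine how comparative effectiveness varies as a function of telemedicine program features (such as patient technical assistance and provider training"). The method is in Section F, Heterogenous Treatment Effects: "we will use the Aim 1 survey for stratified analyses of telemedicine factors, such as historical use of telemedicine and patient technical assistance". The same paragraph adds: "We will use the same analytic approach described in the primary analysis to conduct these subgroup analyses". It also plans "univariate subgroup analyses with interaction effects to statistically test for differences in outcomes" among the subgroups.

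The primary approach, in Section F, Primary Analysis, compares patients at clinics that switched to telemedicine-only visits with "patients at comparable clinics that have not or that used a mixture of telemedicine and in person care". Section E, Interventions and Comparators, describes the comparison group in the same way: "patients that are attributed to clinics that delivered telemedicine-supplemented in-person visits or in-person visits only during the pandemic".

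Neither section says where an in-person-only clinic goes when the stratifying feature belongs to a telemedicine program. Neither says that the feature analyses are confined to the telemedicine arms or use one fixed comparator.

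**The concern.** A clinic that runs no telemedicine has no technical assistance or provider training for it. Splitting all clinics on such a feature therefore splits the comparator unevenly. Mixed-care clinics can fall on either side. In-person-only clinics can fall only on the without side, or nowhere.

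Two consequences follow. The contrast with in-person-only care, which the closing paragraph of Heterogenous Treatment Effects discusses, has an empty or nearly empty cell in the with-feature stratum. If the comparator is pooled instead, the two strata answer different questions: one compares telemedicine-only with mixed care, the other compares it with a blend of mixed and in-person-only care. The difference between strata then combines the feature's effect with the change of comparator.

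Aim 2B is the part of the study meant to show which implementation choices support telemedicine. An artefact of this kind could wrongly credit or discredit technical assistance or training.

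**Working it through.** **Plan's own figure.** The documents give no number for the Aim 2B analysis. The nearest anchor is the non-inferiority power in Section E, Power Calculation: 25,000 per group, a 1-point margin, one-sided 2.5%, ED rates of 20% to 5%, and stated power of 80% to 99%. With power = Φ(0.01/√(2p(1-p)/25,000) - 1.96):
- p = 0.20: Φ(2.795 - 1.96) = 79.8%.
- p = 0.05: Φ(5.130 - 1.96) = 99.9%.

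The figure reproduces and is not disputed. It supplies the group size and ED rates used below.

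**Gap between strata when the feature has no effect.** Let dT and dM be the effects of telemedicine-only and mixed care against in-person-only care, in percentage points of ED use. Let s be the in-person-only share of the without-feature comparators. Assume in-person-only clinics are placed in the without-feature stratum.
- With-feature contrast: dT - dM.
- Without-feature contrast: dT - (1 - s)·dM.
- Gap (with minus without): -s·dM.

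The term dT cancels. Assumed inputs: dT = 1.0; dM = 0.5 or 0.8; s = 0.25, 0.50, 0.75.

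| s | With (dM 0.5) | Without (dM 0.5) | Gap (dM 0.5) | Gap (dM 0.8) |
|---|---|---|---|---|
| 0.25 | 0.50 | 0.63 | -0.13 | -0.20 |
| 0.50 | 0.50 | 0.75 | -0.25 | -0.40 |
| 0.75 | 0.50 | 0.88 | -0.38 | -0.60 |

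**How often a test would be misled.** Assume three equal arms of 25,000, dM = -1 point, and a share q of telemedicine-using clinics with the feature. Then s = 1/(2 - q). A simple post-period difference stands in for the event-study estimate. The variance of the gap is p(1-p)·[2/(25,000q) + 1/(25,000(1-q)) + 1/(25,000(1-q) + 25,000)]. The clustered case multiplies this by 1 + (25,000/83 - 1)·0.01 ≈ 4.0. It assumes an intraclass correlation of 0.01 and about 83 clinics per arm (the 250 target practices divided by 3). The last four columns give two-sided 5% rejection rates for a feature with no effect.

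| q | s | Gap | ED 20%, no clustering | ED 5%, no clustering | ED 20%, clustered | ED 5%, clustered |
|---|---|---|---|---|---|---|
| 0.25 | 0.57 | +0.57 | 11% | 26% | 6.5% | 10% |
| 0.50 | 0.67 | +0.67 | 18% | 47% | 8% | 16% |
| 0.75 | 0.80 | +0.80 | 21% | 57% | 9% | 19% |

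A simulation (4,000 runs, q = 0.5, no clustering) gave 18% at the 20% ED rate and 54% at the 5% rate. When the comparator had the same composition in both strata, the gap was about zero and rejection was 4.9% to 5.7%. With dM = 0 it was about 5%. Clustering lowers the rejection rate but leaves the gap itself unchanged.

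**Does matching rescue it?** The clinic characteristics listed for the propensity score do not include program features, and no matching or weighting can fill a cell that contains no clinics.

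**The case against.** Several points on the other side are sound and limit the finding.

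- A reader might infer that none of the named factors can exist in an in-person-only clinic. That is wrong for historical use of telemedicine: Section C, Outcomes and Covariates, collects pre-COVID experience as a practice characteristic, which any clinic can have.
- A reader might infer that the with-feature stratum must contain no clinic from the in-person-only arm. Section E sets arms at the onset of the pandemic and allows clinics to change later, so a few could report a feature afterwards. They would be later adopters, not a representative in-person-only group, so largely or wholly absent is the supportable wording.
- The documents do not say that in-person-only clinics are coded as lacking the feature. The changing comparator follows from a literal reading with pooling. Under pairwise contrasts, telemedicine-only versus mixed care is clean in both strata, and the in-person contrast is visibly missing in one.
- The interaction test may not reach these factors. The sentence points to subgroups outlined afterwards, and those named are race/ethnicity, rurality and income.
- The plan elsewhere compares programs with each other: the visit-share quartiles in Primary Analysis are formed within the telemedicine arm. But that rule covers dose, and nothing extends it to the feature strata.

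What remains is that the stated method for program-dependent features gives either an inestimable contrast or a shifting one. Reusing all in-person-only clinics as a common reference would be sound, but the plan does not say this, and stratifying on the feature does not do it.

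**Conclusion.** The point holds for features that presuppose a telemedicine program: patient technical assistance and provider training among those named. For these, the stratified analysis does not give a like-for-like contrast in each stratum. Under pooling with in-person-only clinics placed in the without-feature stratum, the artefact is -s·dM: -0.13 to -0.38 point at an assumed dM of 0.5, -0.20 to -0.60 at 0.8, and zero if mixed and in-person-only care have equal outcomes. The plan's overall hypothesis is that the three groups differ, so equality is not a safe default. The values of dM, s, q, the intraclass correlation and the equal arms are all assumptions. The direction of the artefact depends on the sign of dM.

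A reader might take this as a threat to the main result. It is not: Section E places exploration of heterogeneity across organizational subgroups among additional secondary analyses, and the primary estimate is unaffected. The point should be fixed because Aim 2B is a named sub-aim.

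**What to change.** In Section F, Heterogenous Treatment Effects, for program-dependent features, replace stratification with a feature-by-arm exposure: telemedicine-only with and without the feature, mixed care with and without it, and in-person-only. Compare every level with the same full in-person-only group. Report the Aim 2B effect as with minus without inside each telemedicine arm; in that difference the common reference cancels, so no change of comparator can enter. Keep ordinary stratification for historical use and any other feature that every clinic can have. State which features fall in each class before results are seen.

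The cost is SAP wording and a recoded exposure variable, with no new data. The cells are smaller and the feature contrasts less precise.

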In order to further improve the comparability of clinics across each of the treatment arms, we will use propensity scores to match clinics based on clinic-level characteristics, including rurality; size; mean clinical risk (HCC score, Elixhauser comorbidity index); and proportions of patients with Medicaid coverage, dually eligible for Medicaid and Medicare, 65 and older, male, and black or Hispanic. In an additional sensitivity analysis, we will exclude patients who tested COVID-positive. We will match clinics based on their baseline characteristics in the pre-pandemic period and their initial treatment arm status after the onset of the pandemic. In addition, we will explore the sensitivity of our estimates to re-matching each month, since, as noted in the intervention section above, treatment status will be time-varying. As part of our descriptive analysis, we will evaluate how often clinics switch treatment arms from their initial treatment status, which will inform our sensitivity analyses.

We recognize that it is possible that the matching procedure might result in the loss of clinics and sample size. If it does, we would instead apply alternative methods that accomplish the goal of propensity score matching (addressing confounding to improve causal estimation) without loss of sample size. The first alternative is inverse probability weighting, which uses the propensity score to re-weight the outcomes, creating a pseudo-sample in which exposure to the intervention is unrelated to potential confounders.⁴¹ The second alternative is doubly robust estimation, which incorporates (i) a propensity score model and (ii) an outcome regression model in order to gain efficiency (more power) in comparison to an inverse weighting, and to reduce reliance on the ability of correctly positing the propensity score model.⁴² We can substitute these approaches for the originally proposed propensity score weighting, or we can instead apply them in a sensitivity analysis.

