We will define the degree of telemedicine exposure (dose) in two ways. First, based on the comprehensive landscape survey of primary care leaders in [Aim 1](#), we will develop a composite score indicating the robustness of the telemedicine program at each clinic site under study. Among other features, this score will take into account the total number of components and delivery modes of the telemedicine program, its focus on providing coordinated care to a patient population with chronic care needs, and staff and clinical support from the organization.

Second, we will define telemedicine exposure based on the proportion of all visits at a given clinic that are delivered via telemedicine in each month. Specifically, we will classify clinics into quartiles of telemedicine exposure based on the distribution of all telemedicine provision among clinics in this treatment arm. We will then separately analyze the relationship between our outcomes of interest and the amount (dose) of telemedicine being offered at a clinic. We will cluster all primary and secondary analysis at the clinic level, as this is the level at which the exposure occurred.⁴³

Finally, in addition to the primary intent-to-treat analysis, we are proposing an additional secondary analysis. This secondary “as treated” analysis is designed to evaluate the relationship between patient-level telemedicine exposure and our outcomes of interest. In this secondary analysis, we will characterize patients’ exposure to telemedicine after the first wave of shelter-in-place measures were put into place based on the treatment that they actually received

PRINCIPAL INVESTIGATOR: [name]; [name]

rather than based on the availability of telemedicine at the primary care clinic to which they were attributed. In this analysis, we will adjust for observed clinic and patient-level characteristics as described in the response above that may impact both the availability and choice to use telemedicine, as well as patient outcomes. Additionally, we will provide estimates from a fixed effects model in which each patient serves as their own control.

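### Patient-level subgroup interactions rest on clinic-wide matching alone, so case-mix gaps inside a subgroup can bias them if the pandemic change in outcome depends on patient risk

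*Combined protocol and SAP*

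**What the plan says.** Section F, Primary Analysis, sets the matching at clinic level: "we will use propensity scores to match clinics based on clinic-level characteristics". The covariates are rurality, size, mean HCC and Elixhauser scores, and "proportions of patients with Medicaid coverage, dually eligible for Medicaid and Medicare, 65 and older, male, and black or Hispanic". All of them describe the clinic as a whole. None is defined within a subgroup, and no patient-level covariate is named for the intent-to-treat model. Patient-level adjustment appears only for the secondary as-treated analysis: "In this analysis, we will adjust for observed clinic and patient-level characteristics".

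Heterogenous Treatment Effects lists "pre-specified sociodemographic subgroups (race/ethnicity, rurality, median income for zip code) and clinical subgroups", and adds dual eligibility and stratification by Aim 1 telemedicine factors. The method is given as "We will use the same analytic approach described in the primary analysis to conduct these subgroup analyses", followed by "We will also conduct univariate subgroup analyses with interaction effects to statistically test for differences in outcomes".

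The primary findings are to be shown with descriptive statistics on "balance across relevant covariates before and after matching". The plan does not say that balance, or the pre-pandemic trend test, will be shown by subgroup level. Inverse probability weighting and doubly robust estimation are offered mainly in case matching loses clinics; neither is described with subgroup-specific or patient-level covariates.

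**The concern.** Equal clinic-wide averages do not make arms comparable inside a subgroup. If matching equalizes both the mean risk score and the subgroup's share of patients, any gap between arms inside the subgroup must be offset by an opposite gap among the other patients. The two cancel in an overall balance table and add together in the arm-by-subgroup interaction.

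Difference-in-differences removes stable level differences. It does not remove a pandemic change that is larger for sicker patients. The pre-pandemic trend test cannot detect a shock that starts with the pandemic.

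Aim 2C and the stated hypothesis that disadvantaged groups gain less from telemedicine depend on these interactions. Section G (Dissemination Policy) also intends the findings to show which patient groups gain most, so that providers can target their programs. A case-mix difference could be read as unequal benefit, in either direction.

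**Working it through.** The plan states no figure on this point, so there is nothing to reproduce. The only yardstick is the 1% ED difference in Power Calculation, read here as 1 percentage point. Its 93% power cannot be recomputed, because no baseline rate or arm split is given.

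**Formula.** Let p be the subgroup's share (equal in both arms), g the between-arm gap in mean HCC inside the subgroup, and b the pandemic fall in ED use, in percentage points per HCC unit. The true telemedicine effect is zero.

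- Equal overall means force a gap of −g·p/(1−p) in the complement.
- Subgroup contrast: −b·g. Complement contrast: +b·g·p/(1−p).
- Overall contrast: p(−b·g) + (1−p)·b·g·p/(1−p) = 0.
- False interaction, in absolute size: b·g/(1−p).

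Equal shares are a fair premise for race/ethnicity and dual eligibility, since those shares are matching covariates. Zip-code income is not one, so exact cancellation is not forced there, although a gap inside the subgroup remains possible.

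**No risk-dependence.** If the pandemic shifts everyone by the same absolute amount, b = 0 and the bias is zero in every subgroup.

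**Example at the large end** (assumed: p = 0.30; subgroup/complement HCC 1.60/1.00 in one arm and 1.18/1.18 in the other; b = 2).

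- Overall mean in the first arm: 0.3 × 1.60 + 0.7 × 1.00 = 1.18, equal to the other arm.
- Subgroup: −2 × (1.60 − 1.18) = −0.84 points.
- Complement: −2 × (1.00 − 1.18) = +0.36 points.
- Overall: 0.3 × (−0.84) + 0.7 × 0.36 = 0.
- False interaction: −0.84 − 0.36 = −1.20 points.

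**Range at p = 0.30** (g from 0.1 to 0.42, b from 1 to 3): 1 × 0.1/0.7 = 0.14 to 3 × 0.42/0.7 = 1.8 points.

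**Dependence on the ED rate.** The non-inferiority paragraph of Power Calculation takes ED rates of 5% to 20%. With mean HCC 1.18, b = 2 is a fall of 2.36 points: 12% of a 20% rate, but 47% of a 5% rate. Holding the relative fall constant at a 5% rate scales b by 5/20, so 2 becomes 0.5. The example then gives 0.5 × 0.42/0.7 = 0.30 points, and the range becomes 0.25 × 0.1/0.7 = 0.04 to 0.75 × 0.42/0.7 = 0.45 points.

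**Dependence on the share** (assumed: ED risk of 10% per HCC unit and a 30% proportional fall, so b = 3; g = 0.2): 3 × 0.2/0.8 = 0.75 points at p = 0.20, 0.86 at p = 0.30 and 1.2 at p = 0.50.

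**False rejection of the 5% interaction test**, by simulation (assumed: 60 clinics per arm, 400 or 800 patients per clinic, clinic shock SD of 1 point, clinic-level t-test). Ranges span both clinic sizes and repeated runs.

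| ED rate | HCC gap | Rejection |
|---|---|---|
| 20% | 0.1 | about 5–7% |
| 20% | 0.2 | about 8–11% |
| 20% | 0.42 | about 17–32% |
| 5%, same relative fall | 0.1–0.42 | about 5–11% |

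At the 20% rate the overall test stays near 5%. At the larger gaps there, rejection is higher with 800 patients per clinic than with 400, because the bias does not shrink with sample size.

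**The case against.** The strongest case against has five parts.

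- **The text is silent rather than committed.** Using the same approach could mean recomputing clinic means among the subgroup's patients and re-matching. The balance statement does not say at what level balance is shown. This stands: a reader might infer that the plan fixes the primary matched set for every subgroup, but it does not say so. It equally names no subgroup-specific covariates, and repeating the match on the same clinic-wide covariates would give essentially the same clinics.
- **The bias needs two conditions that the documents do not show.** After matching on risk and on payer, age, sex and race shares, arms must still differ in subgroup-specific case mix, and the shock must depend on risk. The plan expects the switch to telemedicine to be potentially unrelated to outcomes and clinic quality. This stands as a limit on likelihood and size. Yet the plan adds matching on mean risk despite using difference-in-differences, so it already treats risk mix as worth balancing; the same reasoning applies inside subgroups.
- **The −1.20-point example is extreme.** It sets a 0.60 HCC difference between subgroups in one arm and none in the other, at the top of the ED range. This stands. A reader might take it as the expected bias, and nothing in the documents supports that.
- **Not every subgroup is equally exposed.** Aim 1 program features are clinic-level, rurality is a matching covariate, and stratifying by illness burden restricts risk variation directly. This stands.
- **Separate matching per subgroup level has its own cost.** It can select different clinics at each level and lose the within-clinic contrast that cancels shocks shared by both subgroups. This stands and shapes the fix.

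**Conclusion.** The point holds as a cheap improvement to the interaction analyses for patient-level subgroups, chiefly race/ethnicity, zip-code income and dual eligibility. It is not a fault in the overall arm comparison, where the offsetting gaps cancel.

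The mechanism follows from the algebra once two conditions are granted: unequal case mix between arms inside the subgroup, and a pandemic change that depends on patient risk. Without the second, the bias is zero. For a 30% subgroup the false interaction is 0.04 to 1.8 points across the assumptions shown. The upper part is comparable with the plan's 1-point ED difference; near a 5% ED rate it stays at or below 0.45 points. The HCC gaps, slopes, shares and clinic numbers are all assumptions.

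A reader might infer that the planned disparity results will be wrong, or wrong in a known direction. The documents do not support that. They support only that the plan, as written, could neither detect nor remove this bias.

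**What to change.** In Heterogenous Treatment Effects:

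1. State that the matched (or weighted) clinic set is common to all levels of a subgroup factor, so that the within-clinic contrast is kept.
2. Add patient baseline HCC score, age band and sex, each interacted with calendar month, to the subgroup interaction models. Optionally, add subgroup-specific clinic means to the propensity or weighting model.
3. Beside each interaction, report arm balance and pre-pandemic trends within each subgroup level, and interpret with caution where balance is poor. A fixed cut-off for the standardized difference is not needed; a value such as 0.1 would be convention, not derived from this study.

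Separate matching within each subgroup level should not be the default.

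The cost is SAP wording and code. The analytic files are already patient-month records, and mean HCC at clinic level already requires patient scores. The downside is somewhat more analysis and somewhat wider intervals for sparse subgroups. The added terms address measured risk only; a gap in unmeasured case mix would remain.
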